5.1 Study treatment

5.1.1 Investigational and control drugs

All subjects will receive a placebo drug-device combination product. The placebo is provided in hard capsules containing 20 mg of placebo particles consisting of DSPC and calcium chloride. Each subject will receive a monthly pack containing:

- One reserve Podhaler device in its case
- One full PI (with the IFU incorporated)
- Four weekly packs, each containing
 - One Podhaler device in its case
 - Seven blister cards, each blister card containing eight placebo capsules
 - One PIL, which contains the IFU

Although only one dose is to be used by each subject, a monthly pack is provided in order to simulate the package that patients would receive when a prescription is filled. The following changes to the artwork and graphics will be made to comply with clinical study labeling requirements:

- a label will be attached to the monthly pack, each weekly pack, blister card and inhaler case indicating clinical trial number and caution statement
- the statement “28 mg per capsule” on the monthly pack, weekly pack and blister card will be replaced with “placebo capsule”

5.1.2 Additional treatment

No additional treatment beyond placebo is included in this study.

5.2 Treatment arms

This is a single arm study and all subjects will be assigned to placebo. The dose regimen for the test product is the contents of four capsules of placebo (i.e. one dose) inhaled via the Podhaler device.

5.3 Treatment assignment

At enrollment, all eligible subjects will be registered via Interactive Response Technology (IRT). The investigator or his/her delegate will contact the IRT after confirming that the patient fulfills all the inclusion/exclusion criteria. In case a subject does not qualify, he/she can be re-screened at a later time point.

It is estimated that approximately 50 subjects will be enrolled with the aim of having 45 subjects completing the study including approximately 15 in each age group as follows: 6-10, 11-17 and ≥ 18 years. Recruitment will be controlled by IRT taking subject age into account.

5.4 Treatment blinding

Not applicable.

5.5 Treating the patient

Sponsor qualified medical personnel will be readily available to advise on study related medical questions or problems.

5.5.1 Patient numbering

Each patient is uniquely identified by a Subject Number assigned by the Sponsor. The Subject Number is composed of a site number and a sequential number. Once assigned to a patient, the Subject Number will not be reused.

Upon signing the informed consent form or, parent/guardian consent and where applicable pediatric assent, the patient is assigned the next sequential number available in electronic data capture (EDC) system. The investigator or his/her staff will contact the IRT and provide the requested identifying information for the patient to register them into the IRT. The site must select the CRF book with a matching Subject Number in the EDC system to enter data. If the patient fails to start the inhalation of the study medication for any reason, the IRT must be notified within 2 days that the patient was not started. The reason for not being enrolled will be entered on the appropriate CRFs capturing screening and demography information.

5.5.2 Dispensing the study drug

Each study site will be supplied with study drug in packaging of identical appearance.

Each subject will receive the same study drug. The study drug packaging will have one label with the medication number.

5.5.3 Handling of study and additional treatment

5.5.3.1 Handling of study treatment

Study treatment must be received by a designated person at the study site, handled and stored safely and properly, and kept in a secured location to which only the investigator and designees have access. Upon receipt, all study treatment must be stored according to the instructions specified on the labels. Clinical supplies are to be dispensed only in accordance with the protocol. Technical complaints are to be reported to the respective the Sponsor's Quality Assurance department.

Medication labels will be in English and comply with the legal requirements of the US. They will include storage conditions for the study treatment but no information about the patient except for the medication number.

The investigator must maintain an accurate record of the shipment and dispensing of study treatment in a drug accountability log. Monitoring of drug accountability will be performed by monitors during site visits or remotely and at the completion of the trial. Subjects will be asked to return all unused study treatment and packaging at the end of the study or at the time of discontinuation of study treatment.

At the conclusion of the study, and as appropriate during the course of the study, the investigator will return all unused study treatment, packaging, drug labels, and a copy of the completed drug accountability log to the Sponsor's monitor or to the Sponsor's address provided in the investigator folder at each site.

5.5.3.2 Handling of additional treatment

Not applicable.

5.5.4 Instructions for prescribing and taking study treatment

The TOBI Podhaler with placebo drug will be dispensed by the investigator during the HF assessment session. Each subject will receive a full monthly pack matching the commercial monthly pack with the exception that placebo capsules instead of active capsules will be used (See [Section 5.1](#)). The site will NOT assist the subject with this inhalation at the site during this visit. Subjects will be given the opportunity to familiarize themselves with the study materials before performing the inhalation. Caregivers will be given the information – as provided in the PI and PIL – that they should help children who are 10 years of age and younger to use TOBI Podhaler and should keep watching them use their TOBI Podhaler until they are able to use it the right way without help. Caregivers of subjects aged 11 and over will be asked to give whatever support they would in reality provide to the subject in preparing and administering a new medication.

The capsule containing the placebo inhalation powder has to be released from the blister card, inserted into the Podhaler device, actuated and the placebo inhalation powder inhaled. Upon completion of this process, the next hard capsule (four in total) shall be removed from the blister card.

Administration of any other inhaled medications should be taken, and any chest physiotherapeutic measures should be completed prior to administration of study treatment. Also, the examinations which should be performed before study drug inhalation ([Figure 3-1](#)) need to be completed prior to study drug administration.

All study medication prescribed and dispensed to the subject must be recorded on the CRF.

The subject should be instructed to inform the investigator and HF Interviewer if he/she is unable for any reason to take the study drug as prescribed.

5.5.5 Permitted dose adjustments and interruptions of study treatment

Dose adjustments and/or interruptions are not permitted. Study drug can only be dispensed and administered on the same day so interruptions for 1 day or more are not permitted.

5.5.6 Rescue medication

Since no active drug is planned to be administered, no rescue medication is needed in this study.

5.5.7 Concomitant medication

This study is a single visit study and it is expected that all study procedures will be completed in few hours. In the event a subject needs to take any medication at the site after enrollment

and/or during the study assessments (for e.g. for treatment of an emerging AE), the patient must notify the study site. All medications, procedures and significant non-drug therapies (including physical therapy and blood transfusions) administered after the patient is enrolled into the study must be recorded in the appropriate CRF.

5.5.8 Prohibited medication

All concomitant treatments are allowed at the investigator's discretion.

Subjects and caregivers with previous experience with the Podhaler device are not eligible for participation in this study.

5.5.9 Emergency breaking of assigned treatment code

Not applicable. This is an open-label study.

5.6 Study completion and discontinuation

5.6.1 Study completion and post-study treatment

The study will be considered completed for an individual subject when the subject completes the HF assessments.

Enrollment will be stopped when sufficient subjects have been recruited to achieve the intended population of 45 completed subjects in total (target of 15 subjects in each of the three age groups). Screened subjects will not be enrolled when the enrolled estimates have been reached to reach the target of 45 completed subjects.

The investigator will make sure appropriate medical care is being provided for all subjects who are prematurely withdrawn from the study.

5.6.2 Discontinuation of study treatment

Discontinuation of study treatment for a patient occurs when study drug is stopped earlier than the protocol planned duration, and can be initiated by either the patient or the investigator. In this single visit study, discontinuation will occur if the subject does not complete the inhalation of the 4 placebo capsules and/or the HF interview.

The investigator must discontinue study treatment for a given patient if, on balance, he/she believes that continuation would negatively impact the risk/benefit of trial participation. Study treatment must be discontinued under the following circumstances:

- Patient wish
- Any situation in which study participation might result in a safety risk to the patient
- Non-compliance of the subject with study procedures or investigator instructions, as per the investigator's judgment
- Emergence of Adverse Events (AE) when worsened from study entry or any newly occurring development of AEs
- Any other protocol deviation that results in a significant risk to the subject's safety

Subjects who are prematurely withdrawn from the study will be replaced by an equal number of newly enrolled subjects to meet the intended target of 15 subjects in each of the three age categories i.e., 45 completed subjects. However, premature withdrawal does not necessarily mean that the subject has failed to complete the HF assessment. It is possible in certain circumstances that subjects could demonstrate the ability to use TOBI Podhaler and carry out the dosing task without using all four capsules; for example, a 6 year-old child may not demonstrate sufficient attention or patience for the entire dose to be taken.

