ICH	International Conference on Harmonization of Technical Requirements for Registration of Pharmaceuticals for Human Use
IEC	Independent Ethics Committee
IFU	Instructions for use
IRB	Institutional Review Board
IRT	Interactive Response Technology
MedDRA	Medical dictionary for regulatory activities
NDA	New drug application
PI	Prescribing Information
PIL	Patient Information Leaflet
PMR	Post-marketing Requirement
PSRM	Product Safety & Risk Management
REALM-SF	Rapid Estimate of Adult Literacy in Medicine-Short Form
SAE	Serious Adverse Event
SAF	Safety Set
SOC	System Organ Class
TIP	Tobramycin Inhalation Powder
TIS	Tobramycin Inhalation Solution
US	United States
WHO	World Health Organization
WoC	Withdrawal of Consent

Glossary of Terms

Close calls	Instances in which a user has difficulty or makes a use error that could result in harm, but the user takes an action to “recover” and prevents the harm from occurring.
Critical tasks	Critical tasks are defined as “the tasks that, if performed incorrectly or not performed at all, would or could cause serious harm”.
Dosage	Dose of the study treatment given to the patient in a time unit (e.g. 100 mg once a day, 75 mg twice a day)
Electronic Data Capture (EDC)	Electronic data capture (EDC) is the electronic acquisition of clinical study data using data collection systems, such as Web-based applications, interactive voice response systems and clinical laboratory interfaces. EDC includes the use of Electronic Case Report Forms (eCRFs) which are used to capture data transcribed from paper source forms used at the point of care.
Enrollment	Point/time of patient entry into the study at which informed consent must be obtained (e.g. prior to starting any of the procedures described in the protocol)
Human factors study	Is the study of designing equipment and devices that fit the human body and its cognitive abilities
Instructions for use	Is a set of written and illustrated steps describing how to use TOBI Podhaler. The instructions for use are included in each weekly pack.
Investigational drug	The drug whose properties are being tested in the study; this definition is consistent with US CFR 21 Section 312.3 and is synonymous with “investigational new drug” or “investigational medicinal product.”
HF Interviewer	A qualified person will conduct the HF assessment sessions (assessment of TOBI Podhaler use and post-use interview).

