6.1 Information to be collected on screening failures

Subjects who are screened but are recognized to have not met all inclusion and exclusion criteria will be considered as screening failures. The study completion page for the screening period will be completed and data on demographics, inclusion/exclusion, and serious adverse event (SAE) will be collected for these patients. Adverse events that are not SAEs will be followed by the investigator and collected only in the source data.

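### Do the completion, replacement and enrollment rules leave users with a short or unstarted dose without a clear status, and the human factors percentages without a denominator?

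*Protocol*

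**What the plan says.** **Short dose.** Protocol 5.6.2 states that "discontinuation will occur if the subject does not complete the inhalation of the 4 placebo capsules and/or the HF interview", and then that "Subjects who are prematurely withdrawn from the study will be replaced by an equal number of newly enrolled subjects", the aim being 15 completed subjects per age group and 45 in all. The same paragraph adds that premature withdrawal need not mean the HF assessment is incomplete: in some circumstances "subjects could demonstrate the ability to use TOBI Podhaler and carry out the dosing task without using all four capsules". Section 5.6.1 gives the completer rule: "The study will be considered completed for an individual subject when the subject completes the HF assessments". Appendix 5, item 18, treats use of fewer than four capsules as a potentially critical use error.

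**Unstarted dose.** Section 5.5.1 reads "If the patient fails to start the inhalation of the study medication for any reason, the IRT must be notified within 2 days", followed by "The reason for not being enrolled will be entered on the appropriate CRFs capturing screening and demography information". The Glossary defines enrollment as "Point/time of patient entry into the study at which informed consent must be obtained", and Section 5.3 places it at IRT registration of eligible subjects; both come before dosing. Section 6.1 says "Subjects who are screened but are recognized to have not met all inclusion and exclusion criteria will be considered as screening failures". The Safety Set (Protocol 9.1, SAP 2.2) needs the contents of at least one capsule to have been inhaled, and SAP 2.3 reports completed and discontinued counts for that set only.

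**Denominator.** Section 9 promises the number and percentage of subjects with each response on each checklist item, with figures per age group where relevant. Only a Screen Failure Set and a Safety Set are defined. Section 13.9 speaks of evaluable data without defining the term, and SAP 1 puts HF analysis outside its scope.

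**The concern.** Use errors and close calls are the only primary variable. Using fewer than four capsules, or being unable to open the case or free a capsule, is therefore an outcome and not merely a reason for missing data. If such a user is labelled a discontinuation and replaced, or labelled never enrolled, the replacement rule could select on the outcome: the 45 counted would be the users who managed, and the percentages would look better than the product deserves.

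The example in 5.6.2 sharpens the worry, because it describes a short dose as compatible with a completed HF assessment when the subject has shown the ability to use the product. That could be read as making completer status depend on success. Without a stated HF set, nothing in the two documents names who is in the percentages.

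**Working it through.** **1. The plan's own figures.** 3 age groups × 15 = 45 completers. The planned enrollment of about 50 implies an allowance of 1 − 45/50 = 10%, and 45/(1 − 0.10) = 50. Both figures reproduce. The 10% is implied, not stated.

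**2. Short dose, passages side by side.**
- 5.6.1 sets one condition for completion, finishing the HF assessments. It names no minimum number of capsules and no requirement that use succeed.
- 3.1 says the end of the interview is the end of both the HF assessment and the study.
- 13.10.1 sends every case of fewer than four capsules to root-cause discussion.
- So a user who stops early by mistake and finishes the interview is a completer under 5.6.1, whatever the treatment-discontinuation label.
- The stated purpose of replacement in 5.6.2 is to reach 45 completed subjects. It fills missing completers and does not tell anyone to delete data.
- The passage about ability to use the product, with its example of a 6-year-old, is an illustration. No section makes it a criterion.
- If such a user were replaced as well, the result would be one extra subject in a group planned as approximately 15.

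**3. Unstarted dose, what is on record.**
- The IRT is told, and the reason goes on a CRF (5.5.1).
- The checklist covers preparation as well as use (3.2.1), and reasons for premature withdrawal are recorded on it (3.2).
- Appendix 5, items 1, 5 and 6, scores failures that occur before inhalation.
- Section 9 analyses all subject data and lists all errors at each task step by participant.
- The SAP 2.3 table would omit this user, but the count can be recovered: subjects registered in the IRT as eligible, minus those in the Safety Set.

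**4. How much the denominator matters.** Assume k short-dose users and no other failure on the four-capsule item. There are two ways of keeping them in: with their replacements, k/(45 + k); or counted among the 45, k/45.

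| k | k/(45 + k) | k/45 | Difference (points) |
|---|---|---|---|
| 1 | 1/46 = 2.2% | 1/45 = 2.2% | below 0.1 |
| 3 | 3/48 = 6.25% | 3/45 = 6.7% | 0.4 |
| 5 | 5/50 = 10.0% | 5/45 = 11.1% | 1.1 |

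Exact (Clopper-Pearson) 95% intervals at k = 5 are 3.3–21.8% and 3.7–24.1%. With all of k = 3 in one age group, 3/18 = 16.7% (3.6–41.4%) against 3/15 = 20.0% (4.3–48.1%). The differences are small beside the imprecision. The plan calls for no intervals; they are shown only for scale.

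The opposite effect is also small. If one user stops at pack opening, and 2 of the 15 who reach a later step fail it, the rate is 2/15 = 13.3% among those who reached it, or 2/16 = 12.5% with the early stopper included.

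Only dropping the failing users altogether would give 0/45. That runs against Section 9, which analyses all subject data, and against 13.6.2, which requires errors with associated criticality to be recorded and fully reported.

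**5. Precedent.** Section 13.5.2 describes the earlier IFU study in 45 untrained, device-naïve CF patients. It reports 31 who emptied all capsules and 14 who did not (31 + 14 = 45; 14/45 = 31.1%). The 14 include failures put down to not engaging with the IFU and to a child who was not inhaling. Failing users stayed in the denominator. That summary does not say how withdrawals were handled.

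**The case for a change.** The best case for a change is this. The study exists to find users who cannot operate the product. A user who is handed the pack and never inhales is among the most informative, yet that user is neither a screening failure by 6.1 nor a member of the Safety Set, and so is neither completed nor discontinued in SAP 2.3. The item percentages are planned output on the primary variable for a regulatory post-marketing requirement, and a listing of errors does not say who belongs in a percentage. Neither document cites an HF plan that does. A few sentences would settle it.

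Three parts stand. The not-enrolled label in 5.5.1 conflicts with the Glossary and 5.3; SAP 2.3 leaves out an eligible user who inhaled nothing; and the HF denominator is unnamed. They are gaps in wording that a competent analyst fills. The SAP tables are supplementary clinical information, and the HF analysis is done independently by the HF vendor, whose own plan may state the denominator. Nor is there one obvious denominator to write in. Counting only users who reached a step conditions on success at earlier steps, while counting everyone dilutes the later ones.

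The part that does not stand is that completion depends on successful use; 5.6.1 contains no such condition.

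**Conclusion.** No change follows. Completer status is settled by 5.6.1, and short or failed use is investigated, scored and listed whatever disposition label it receives. The enrollment wording in 5.5.1 is a clerical inconsistency. The disposition gap affects one supplementary table, and only if an eligible user inhales nothing. The unnamed denominator moves an overall item rate by about one percentage point for up to five assumed short-dose users, or 16.7% against 20.0% if three fall in one age group.

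This rests on two assumptions. First, the HF vendor follows Section 9 as written, keeping all subject data and listing every error; had failing users been dropped, the rates above would become zero and the concern would be a real one. Second, such users are few. Their number is unknown: the 2011 study reports no failure to use four capsules at its later assessment, but those users were trained and the capsules were empty. With 34 assessed, zero is still compatible with a rate of up to 10.3% (exact 95%). No hypothesis is tested, the protocol gives no pass threshold, and reporting is primarily qualitative, so the study's conclusion does not turn on which sensible denominator is used.

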3.7 Risks and benefits

Besides contributing to the assessment of the user interface that could be of benefit to patients, this trial may not offer a direct benefit to the subjects. Any risk to subjects in this trial will be minimized by compliance with the inclusion/exclusion criteria. No active drug is being administered but there is a potential risk of an allergic reaction from unrecognized sensitization to the placebo content (i.e. DSPC (1, 2-distearoyl-sn-glycero-3-phosphocholine) and/or calcium chloride).

As with all inhaled medications, cough and bronchospasm (asymptomatic or reported as wheeze) may occur; especially in subjects with known or suspected bronchial hyper-responsiveness.

Patients who experience any of these symptoms after dosing should be managed as per standard of care and the events should be recorded as Adverse Events (AEs).

Subjects will also be asked not to continue with any activity that they find painful. If bodily fluid is drawn or expelled, the HF Interviewer and Investigator/designated staff will quarantine the Podhaler device and anything that could have come into contact with the bodily fluid. The room will be sanitized and the subject will be treated as per the investigator decision. All AEs must be recorded on the appropriate CRF capturing AEs.

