6.5 Human factors assessment

The HF assessment is summarized in [Section 3.2](#) and detailed in [Appendix 1](#) and includes the following:

- An interview guide will provide a script for the HF Interviewer ([Appendix 4](#)).
- HF assessment checklist will be a paper form completed both by a qualified trained Interviewer from a specialized HF vendor and by the trained HF Observer. Data capture by two independent assessors will help to ensure accurate and unbiased recording. The checklist is used to collect all of the information required for data analysis on observed performance of use steps and response to comprehension questions. Demographic variables include but are not limited to subject age, gender, previous inhalation device experience, dominant hand, vision and dexterity challenges, health literacy (US school reading grade equivalent), educational attainment, and assistance provided to minors by caregivers during the study. Observed data collected for subject performance of use steps will be marked as pass or fail. Evident close calls will also be noted down. Key points from Interviewer-led discussion will be noted down on the HF Assessment checklists (e.g. observations, opinions of the subject etc.) – with the objective of capturing root cause of use errors and/or subject misunderstandings.
 - HF Assessment sessions will be digitally recorded in audio and video for future reference, and to allow independent checking of study data.
 - The used capsules (including photos) and Podhaler device(s) (if device(s) seem to be defective) will be subject to post-use inspection by the HF Interviewer in order to inform discussion on errors and their root cause.

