7.1 Adverse events

An AE is any untoward medical occurrence (e.g., any unfavorable and unintended sign [including abnormal laboratory findings], symptom or disease) in a subject or clinical investigation subject *after providing written informed consent* for participation in the study until the end of study visit. Therefore, an AE may or may not be temporally or causally associated with the use of a medicinal (investigational) product.

The occurrence of adverse events must be sought by non-directive questioning of the patient at each visit during the study. Adverse events also may be detected when they are volunteered by the patient during or between visits or through physical examination findings, laboratory test findings, or other assessments.

Abnormal laboratory values or test results constitute adverse events only if they fulfill at least one of the following criteria:

- they induce clinical signs or symptoms,
- they are considered clinically significant,
- they require therapy.

Clinically significant abnormal laboratory values or test results must be identified through a review of values outside of normal ranges/clinically notable ranges, significant changes from baseline or the previous visit, or values which are considered to be non-typical in patient with underlying disease. Investigators have the responsibility for managing the safety of individual patient and identifying adverse events.

Adverse events must be recorded in the appropriate CRF capturing AEs under the signs, symptoms or diagnosis associated with them, accompanied by the following information:

- the severity grade
 - mild: usually transient in nature and generally not interfering with normal activities
 - moderate: sufficiently discomforting to interfere with normal activities
 - severe: prevents normal activities
- its relationship to the study treatment
- its duration (start and end dates) or if the event is ongoing an outcome of not recovered/not resolved must be reported.
- whether it constitutes a serious adverse event (SAE - See [Section 7.2](#) for definition of SAE) and which seriousness criteria have been met.
- action taken regarding study treatment

All adverse events must be treated appropriately. Treatment may include one or more of the following:

- [investigational] treatment dose not changed (e.g. further observation only)
- [investigational] treatment dose increased/reduced
- [investigational] treatment interrupted/withdrawn

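### Section 5.6.2 makes any new or worsened adverse event a mandatory stop whatever its severity, so an expected mild cough can end the four-capsule task early

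*Protocol*

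**What the plan says.** Protocol Section 5.6.2 introduces a list with "Study treatment must be discontinued under the following circumstances". One entry is "Emergence of Adverse Events (AE) when worsened from study entry or any newly occurring development of AEs". It has no threshold for severity, seriousness or relatedness. The same section separately requires a stop when the investigator finds the risk/benefit balance unfavourable, and in any situation that might put the patient at risk.

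Section 3.7 states: "As with all inhaled medications, cough and bronchospasm (asymptomatic or reported as wheeze) may occur". Patients with these symptoms "after dosing should be managed as per standard of care and the events should be recorded as Adverse Events (AEs".

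Section 7.1 defines an AE as any untoward sign or symptom after consent, whether or not it is causally linked to the product. Its lowest grade is "mild: usually transient in nature and generally not interfering with normal activities". Among the possible responses to an AE it lists "treatment dose not changed (e.g. further observation only".

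The post-marketing requirement quoted in Section 1.1 asks for conditions representative of realistic use and for all critical tasks to be included. Section 13.6.2 treats under-dosing errors as critical only when they recur routinely. Appendix 5, item 18 covers taking all four capsules.

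**The concern.** The study exists to watch untrained users take a full dose. Coughing and then carrying on is part of ordinary use of a dry powder inhaler. If the first mild cough ends the session's dosing, nobody sees how that user handles the remaining capsules, and item 18 cannot be performed at all.

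Sites also hold two instructions for the same event. One that follows Section 7.1 and observes a mild cough departs from Section 5.6.2. One that follows Section 5.6.2 loses observation that the study was designed to collect, with no stated safety reason.

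**Working it through.** **Step 1: does a mild cough trigger the rule?**

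- Cough on inhalation is foreseen and recorded as an AE (3.7).
- A transient cough that does not interfere with activity is still an AE, graded mild (7.1).
- Any new AE requires a stop (5.6.2).

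So a new mild cough after capsule 1, 2 or 3 ends dosing. There are two limits. A cough already present at entry counts only if it worsens. The phrase about symptoms after dosing in 3.7 could mean after the whole dose, but the AE definition in 7.1 runs from consent, so a cough between capsules is covered.

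**Step 2: what does the bullet add to the other stops?**

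AEs that raise a safety concern are already covered by the separate safety-risk entry and by the investigator's risk/benefit duty in 5.6.2. What the AE bullet adds is AEs without a safety concern.

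**Step 3: what goes unobserved?**

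The IFU asks for two inhalations per capsule (steps 10 to 15) and four capsules (step 18), so 4 × 2 = 8 inhalations. Loading and piercing (steps 7 to 9) are normally done once per capsule.

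| Stop after capsule | Loadings and piercings seen | Inhalations seen | Item 18 |
|---|---|---|---|
| 1 | 1 of 4 | 2 of 8 | not possible |
| 2 | 2 of 4 | 4 of 8 | not possible |
| 3 | 3 of 4 | 6 of 8 | not possible |

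**Step 4: the plan's own numbers.**

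3 groups × 15 = 45 completers (9.8). With about 50 enrolled (Section 4), the implied loss is 1 − 45/50 = 10%, and 45/0.90 = 50. Both figures reproduce. There is no hypothesis test and hence no power to compute (9.4.2).

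**Step 5: size under assumption.**

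The documents give no cough or AE rate, so the share of subjects stopped early, s, is an assumption. Expected users stopped per group of 15 is 15s. Those who attempt all four capsules, if nobody is replaced, number 15(1 − s). Enrolment for 45 full-dose users, if all stopped subjects are replaced, is 45/(1 − s), rounded up.

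| s | Stopped per 15 | Attempt all four | Enrolment if replaced |
|---|---|---|---|
| near 0 | near 0 | about 15 | about 45 |
| 5% | 0.75 | 14.25 | 48 |
| 10% | 1.5 | 13.5 | 50 |
| 20% | 3.0 | 12.0 | 57 |
| 30% | 4.5 | 10.5 | 65 |

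To link s to a rate per breath, let q be the chance of a new AE per inhalation, taken as independent. The first three capsules hold 3 × 2 = 6 inhalations, so s = 1 − (1 − q)^6. This gives 5.9% for q = 1%, 11.4% for q = 2% and 26.5% for q = 5%; s = 10% needs q = 1.7%. These values only show scale. Nothing in the documents fixes q.

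**The case against.** **The strongest case for leaving the text alone.** This is placebo with no direct benefit, given to patients from age 6 with FEV₁ down to 25% of predicted, so cautious stopping is a legitimate choice. Investigators may in practice not apply the bullet to a mild cough. The summary of the previous placebo-powder study in 45 untrained patients (13.5.2) reports that 31 emptied all four capsules and names no AE stop among the reasons given for the other 14. That study's stop rule is not stated, so it does not settle the rate here, but it gives no sign of a large one. These points stand, and they keep the concern small. They do not remove the conflict between 5.6.2 and 7.1.

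**Stronger readings that a reader might infer, and why they fail.**

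- *That 5.5.5 forbids even a pause.* It says "Dose adjustments and/or interruptions are not permitted", but its next sentence concerns interruptions of a day or more, and the Appendix 4 script invites subjects to pause.
- *That the sample size fails.* If every stopped subject needed replacing, the chance that 50 enrolled yield at least 45, from a Binomial(50, 1 − s), is 0.62 at s = 10% and 0.05 at s = 20%. But 50 is described as an estimate (Section 4), withdrawn subjects are replaced one for one (5.6.2), and enrolment runs until 45 completers can be reached (5.6.1). The minimum of 15 in 9.8 counts subjects, not full doses.
- *That repetition is lost altogether.* Inhalation steps repeat within each capsule, and Sections 3.2.2 and 13.6.2 judge likely recurrence from root-cause discussion because one session may not show it.
- *That a stop would count against the device.* "Observed data collected for subject performance of use steps will be marked as pass or fail" (6.5), and one subject in 15 is 6.7 percentage points. But the analysis is primarily qualitative and turns on errors attributable to the interface (9.4). Every case of fewer than four capsules is investigated (13.10.1), which would identify an AE stop.
- *That scoring and counting are left unstated.* The plan provides for replacement and for a partial dose that may still be a completed assessment (5.6.2). It has the withdrawal reason recorded on the checklist (3.2) and errors listed by participant (Section 9). The SAP adds disposition with reasons (2.3) and AEs leading to withdrawal (2.5.1). The checklist form itself is not among the documents, so whether it has a code for such stops cannot be judged.

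**Conclusion.** The point holds for the stop rule alone. As written, 5.6.2 obliges the site to end dosing for an expected, mild and self-limiting event, and 7.1 points the other way. The loss is observation of later capsules and of item 18 in users who cough and could safely continue. Errors seen before the stop are kept, and the interview can still take place.

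The size cannot be estimated from the documents. It ranges from near zero, if the bullet is not applied to mild cough, to an average of 4.5 users per group of 15 at an assumed 30% stop rate. It rests on a literal reading of the bullet and on new or worsened cough occurring before capsule 4. That cough would make later use errors more likely is an inference that the documents do not make, and this conclusion does not depend on it. The change is worth considering because it is cheap; the matter does not threaten the completer target or the study's conclusion.

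**What to change.** Replace the AE entry in Section 5.6.2 with a mandatory stop for:

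- any serious, moderate or severe AE;
- bronchospasm or wheeze, hemoptysis, or allergic symptoms;
- any case in which the investigator judges it unsafe to continue.

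Add that a mild cough that settles is recorded as an AE and is not a mandatory stop. This brings 5.6.2 into line with 7.1. Section 5.5.5 needs no change.

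As an optional clarification, the checklist could carry a code for tasks not attempted because dosing was stopped for an AE, with the number who attempted each task shown as the base for its percentage.

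The cost is a few sentences. Some subjects would inhale further placebo capsules after a mild cough; Section 3.2.1 already has qualified site staff present throughout. If the optional code is used, bases will differ slightly between tasks and must be shown.
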